Assessments will be delivered at baseline, post-treatment, 6-month follow-up and 12month follow-up. At baseline, all participants will be interviewed for their basic demographic and clinical characteristics (age, sex, education, height, weight, current medications etc). Self-administered questionnaires will be completed online to assess depressive symptoms and severity (PHQ-9), anxiety (Generalised Anxiety Disorder 7item, GAD-7⁶⁰), suicidal ideation (Beck Scale for Suicide Ideation, BSSI⁶¹), sleep symptoms (ISI, 7-Day Daily Sleep Diary), daytime symptoms (Multidimensional Fatigue Inventory, MFI⁶²), chronotype (reduced Morningness-Eveningness Questionnaire, rMEQ ⁶³), sleep-related thoughts and behaviors (brief version of dysfunctional beliefs and attitudes about sleep, DBAS-16⁶⁴), circadian rhythms and sleep parameters (7-Day Daily Sleep Diary). During the intervention, participants will additionally complete ongoing assessments to evaluate their sleep symptoms, mood symptoms and sleep parameters (ISI, PHQ-9, GAD-7, 7-Day Daily Sleep Diary) at post-session 2 and post-session 4. Saliva collection kit will be mailed to participants at baseline to collect their salivary cortisol and DNA, and at 12-month follow-up to collect their salivary DNA. After finishing the intervention, each participant will be paid CNY100 (or HKD equivalent) for his or her participation. Part of the participants in e-CBT-I group will be invited to receive semi-structural individual interviews about user experience and satisfaction towards e-CBT-I intervention via phone after intervention, and will be additionally paid CNY100 (or HKD equivalent) for his or her participation.

At post-treatment, 6-month follow-up and 12-month follow-up, participants will receive phone calls from the independent researcher blinded to the randomization status for diagnostic interviews to examine whether they have current insomnia measured by ICD-10 Classification of Mental and Behavioral Disorders, MDD or suicidality measured by MINI. Part of the diagnostic interviews will be audiotaped and second-rated by an independent rater to assess interrater reliability after obtaining participants' consents. In addition, participants will complete online questionnaires similar to those at baseline. After finishing the 12-month follow-up, each participant will be paid CNY50 (or HKD equivalent) for his or her participation.

Outcomes

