The primary outcomes include remission rate of insomnia disorder conformed by ICD-10 Classification of Mental and Behavioral Disorders, change of insomnia symptoms measured by ISI, occurrence of MDD conformed by MINI and change of depressive symptoms measured by PHQ-9. Secondary outcomes include incidence of suicidality which includes plans and attempts as measured by MINI and change of anxiety symptoms measured by GAD-7. Other pre-specified outcome include incidence of suicidal ideation measured by BSSI, change of daytime symptoms measured by MFI, change of sleep-related thoughts and behaviors measured by DBAS-16, change of circadian rhythms measured by 7-Day Daily Sleep Diary and MEQ, and change of sleep parameters including time in bed (TIB), total sleep time (TST), sleep onset latency (SOL), wake after sleep onset (WASO), sleep efficiency (SE) measured by 7-Day Daily Sleep Diary.

Sample Size Estimation

The sample size calculation was based on the occurrence of diagnosed depressive disorder because the primary aim of the current study was to prevent clinical depression. According to the previous meta-analysis, the incidence rate of depression is approximately 11% in the individuals with insomnia ¹⁵. As the study sample included a mixture of individuals without prior depression and those with a history of MDD, an expected 50% increase in the cumulative one-year occurrence of diagnosed depressive disorder is anticipated (16.5%). Based on the previous research on CBT-I and our trial data on sleep-focused treatment for depression, a 50% reduction of occurrence rate is expected for the intervention group. Power analysis using Stata suggested that a total of 282 participants per condition would be required to achieve a power of 0.80 whilst allowing a type I error of 0.05 detect a hazard ratio of 0.5 under 1:1 randomization. In view of the attrition rate from previous study (40%), a total of 940 participants would be required (470 participants in each group x 2 groups). A protocol amendment was submitted to reduce the sample size to 708 (354 per group) based on an estimated attrition rate of approximately 20%, as it was determined that the attrition rate was lower than initially expected.

Data Analysis

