All main analyses will be based on the intent-to-treat (ITT) approach. We aim to obtain full follow-up data on every participant, but missing data may be inevitably expected due to withdrawal, loss-to-follow-up, or non-response questionnaire items. Baseline characteristics will be presented as percentage for categorical variables and as means (standard deviations) for continuous variables. The primary and secondary outcomes with continuous variables will be examined by using linear mixed-effects model (LMM) analysis. The changes of efficacy indicators (e.g., PHQ-9) from baseline to each follow-up time points and intervention differences were tested by the MIXED module of Stata, with major measures at each time point nested within each participant. Interaction effects of group by time will be examined to compare the effects of treatment on the major outcomes. Between-group difference in the estimated mean change from baseline to each time points from mixed models and Cohen's d will be used to calculate effect sizes. Current MDD will be analyzed by the survival analysis and the Mentel-Cog log rank test. An observation will be right censored to the day after the last point of interview when a participant is no longer eligible to experience a depressive episode, e.g., lost to follow-up or completed the trial without experiencing a depressive episode (12month follow-up after intervention). The effect of the intervention on insomnia remission will be analyzed using generalized estimating equations (GEE). The GEE analysis will be conducted by using the XTGEE module of Stata. Mediation analysis using maximum likelihood estimation within a structural equation modeling framework will be used to determine which outcomes are mediated by changes in candidate factors including sleep symptoms, mood symptoms, sleep-related unhelpful thoughts and maladaptive behaviors, circadian rhythm disruption and sleep parameters at follow-up. Sensitivity analyses will be conducted using imputation methods to examine the robustness of the results based on

different assumptions about the missing data. Strata variables (sex and insomnia severity) at baseline will be included as covariates in all analyses. Variables with a p value ≤ 0.05 will be considered statistically significant.

Ethics & Other Considerations

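### The mixed models for ISI, PHQ-9 and GAD-7 compare change from baseline without stating adjustment for each scale's own baseline score, which gives up some precision

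*Combined protocol and SAP*

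**What the plan says.** The Outcomes section lists ISI change and "change of depressive symptoms measured by PHQ-9" among the four primary outcomes, and "change of anxiety symptoms measured by GAD-7" as a secondary outcome. Baseline scores on all three scales are collected (Assessments).

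For these scales the Data Analysis section specifies a linear mixed model in Stata, with each participant's measurements over time nested within the participant. Three sentences define the treatment effect:

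- The quantity analysed is change: "changes of efficacy indicators (e.g., PHQ-9) from baseline to each follow-up time points and intervention differences were tested by the MIXED module".
- The arms are compared through an interaction: "Interaction effects of group by time will be examined to compare the effects of treatment on the major outcomes".
- The effect size, alongside Cohen's d, comes from this quantity: "Between-group difference in the estimated mean change from baseline to each time points from mixed models".

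On covariates it says only: "Strata variables (sex and insomnia severity) at baseline will be included as covariates in all analyses". It does not name the baseline score of the analysed scale as a covariate, does not state whether the arms share a baseline mean, and does not give the within-participant covariance structure.

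**The concern.** If change is estimated from a model of repeated measures, the natural reading is that baseline is one of the responses and each arm has its own mean at every visit, baseline included. With complete data the group-by-time contrast is then the difference between arms in mean change score. Randomisation gives the arms the same expected baseline, and that contrast does not use this fact. Subtracting the whole baseline score is usually less efficient than subtracting the part of it that predicts follow-up.

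At stake is the precision of two primary outcomes and one secondary outcome. Part of any chance baseline imbalance also passes into the estimate. PHQ-9 and GAD-7 are the more exposed, because randomisation is stratified on sex and insomnia severity only (Study Design).

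**Working it through.** **The plan's own figure.** The plan gives no precision figure for these scales. Its only size calculation is for MDD (Sample Size Estimation), and it reproduces. The Freedman log-rank formula with two-sided alpha 0.05 (sidedness assumed), power 0.80 and HR 0.5 gives 7.849 × (1.5/0.5)² = 70.6 events. The event risks are 16.5% and 1 − 0.835^0.5 = 8.62%, mean 12.56%. So 70.6/0.1256 = 562.4 in total, or 281.2 per arm, rounded up to the stated 282. With 20% attrition, 282/0.8 = 352.5, against 354 stated. Nothing below alters these numbers.

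**Variance identity.** Let sb and sf be the baseline and follow-up SDs and r their correlation among trial participants. Per participant:

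- change contrast: sb² + sf² − 2·r·sb·sf
- baseline-adjusted contrast: sf²(1 − r²)
- difference: (sb − r·sf)², which is never negative and is zero only when sb = r·sf

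Ratio, adjusted to planned (r assumed):

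| sb/sf | r = 0.3 | r = 0.5 | r = 0.7 |
|---|---|---|---|
| 1.0 | 0.65 | 0.75 | 0.85 |
| 0.7 | 0.85 | 0.95 | 1.00 |
| 0.5 | 0.96 | 1.00 | 0.93 |

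Example: sb/sf = 0.7 and r = 0.3 gives 0.91/(0.49 + 1 − 0.42) = 0.91/1.07 = 0.85.

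**Effect of the entry criteria.** Entry limits narrow the baseline spread (ISI 15 or above; PHQ-9 above 4 and below 20; current or recent MDD excluded), so the equal-SD row is too favourable for the two primary scales. Simulated selection, assuming a source-population SD of 5 and an unselected correlation of 0.5 to 0.7, gives:

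- PHQ-9, population mean 8 to 11. Window alone: 0.85 to 0.92. With a mild assumed MDD exclusion: 0.88 to 0.94. With stronger ones: 0.90 to 0.96. Overall 0.85 to 0.96, so the true SE is 2% to 8% smaller (1 − √0.96 to 1 − √0.85).
- ISI, population mean 12 to 18, severity cut assumed at 22. Because allocation is stratified by severity, some of the imbalance is already removed by design. The ratio of true variances is 0.95 to 0.98, an SE 1% to 2.5% smaller.
- GAD-7, which has no entry limit of its own, selected indirectly through PHQ-9 and MDD (assumed GAD-7/PHQ-9 correlation 0.5 to 0.7): 0.78 to 0.90, an SE 5% to 12% smaller.

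As equivalent participants (708/ratio − 708), PHQ-9 gains about 30 to 125 and ISI about 14 to 37.

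**Do the planned covariates already do this?** As a main effect, severity shifts a participant's baseline and follow-up alike, so it cancels from the change contrast. For four visits, 282 per arm, r = 0.5, equal SDs and complete data, the SE of the 12-month contrast is 0.0842 SD with or without the stratum term, and 0.0729 SD with a common baseline mean. With 20% dropout the stratum term still hardly moves the SE. If change scores were instead the response, severity would recover about half or more of the ISI gain. It would recover almost nothing for PHQ-9: the ratio stays at 0.91 to 0.95 in the case checked (population mean 9.5, stronger MDD exclusion, PHQ-9/ISI correlation 0.3 to 0.5).

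**Dropout.** With 10%, 15% and 20% lost at the three follow-ups, the 12-month ratios at r = 0.3, 0.5 and 0.7 are 0.69, 0.79 and 0.87 for equal SDs, and 0.87, 0.96 and 1.00 for sb/sf = 0.7. Dropout reduces the gain slightly but does not remove it.

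**Chance imbalance.** The simulated baseline PHQ-9 SDs run from 2.56 to 3.70. With 354 per arm, one SE of imbalance is SD × √(2/354): 0.19 to 0.28 points. The planned contrast carries the share 1 − slope. With a slope of 0.7 to 0.5, that is 0.3 × 0.19 = 0.06 to 0.5 × 0.28 = 0.14 points.

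**Reported interval.** The plan's wording is compatible with a random-intercept model. Taking baseline PHQ-9 SD 2.6 to 3.7, correlation with follow-up 0.5 to 0.7 and correlation between follow-ups 0.5 to 0.8, the adjusted variance under an unstructured covariance is about 0.76 to 1.31 times the variance a random-intercept fit would report for the planned contrast. So the printed interval could narrow or widen, although the true sampling variance falls or is unchanged.

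**The case against.** The planned analysis is standard and valid. The outcomes are defined as change, and the model estimates change by likelihood, under ITT, with the stratification factors included. A common baseline mean is merely unstated. Choosing between two unbiased estimators is a matter of efficiency, the gain on the primary scales is small, and every input to its size is assumed. The reported interval might not narrow at all if the plan means a random-intercept fit.

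Most of this stands. There is no error to correct, the magnitudes are illustrative, and no promise can be made about the width of the printed interval. The carried PHQ-9 imbalance is also small, at about 0.06 to 0.14 points on these assumptions. What does not follow is that nothing should change: the baseline scores are in hand, adjustment cannot raise the large-sample variance, and stating the model in advance closes a choice that the present text leaves open.

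The defence that insomnia severity is already a covariate does not succeed. As a main effect it leaves this contrast as it was, and it is not a baseline score for PHQ-9 or GAD-7. Stratified allocation does help ISI, which is why the ISI gain is put at only 1% to 2.5% of the SE.

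**Conclusion.** The concern holds as a modest loss of precision. On the natural reading of the Data Analysis section, the ISI, PHQ-9 and GAD-7 effects are differences in change with no adjustment for the scale's own baseline. Under the stated assumptions the true-variance ratio is about 0.85 to 0.96 for PHQ-9, 0.95 to 0.98 for ISI and 0.78 to 0.90 for GAD-7. It reaches 1.00 when sb = r·sf.

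Four stronger readings are tempting and not supported:

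- That the planned estimate is biased. Randomisation makes it unbiased.
- That the sample size is wrong. It is set by MDD occurrence and is untouched, as are the MDD and insomnia-remission analyses.
- That the gain on the primary scales is as large as the equal-SD figures (ratio 0.65 to 0.85). The entry limits on ISI and PHQ-9 make equal SDs implausible there.
- That the plan excludes a common baseline mean, or that published intervals will narrow by a known amount. The text is silent on both the baseline constraint and the covariance structure.

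The change is worth making because it costs almost nothing, not because the present plan would mislead.

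**What to change.** In the Data Analysis section, state that each continuous-outcome mixed model adjusts for the baseline score of its own scale, in one of two forms:

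1. *Post-baseline visits are the responses. The model contains group, visit, group-by-visit, the continuous baseline score, baseline-by-visit, sex and insomnia-severity stratum, with an unstructured within-participant covariance. The group difference is reported at each visit.* This keeps the rule that strata enter every analysis. Because "All main analyses will be based on the intent-to-treat (ITT) approach", the text must also say how participants with only a baseline value are handled.
2. *Baseline and follow-up visits are the responses, with one baseline mean common to both arms, a group effect at each post-baseline visit and an unstructured within-participant covariance.* Participants with only a baseline value then stay in the model.

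In either form the group effect at a visit still estimates the between-group difference in mean change, so the outcome definitions need no edit. The cost is a few sentences in the SAP and a small change to the Stata code, covering both the baseline term and the covariance option. No new data are needed and the sample size does not change.

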Youth in e-CBT-I group will have fewer insomnia symptoms, depressive symptoms, suicidal ideation, plans and attempts than those in control group at each timepoint.
 Changes in candidate factors including insomnia symptoms, mood symptoms, circadian rhythms and sleep parameters will mediate the outcomes.

Recruitment and Screening

Potential participants will be recruited from colleges and senior secondary school in Hong Kong and mainland China and will be identified from various sources. These will include the local partner schools in Hong Kong established from our previous research projects. Partner schools in mainland China will be recruited by our collaborators with the school links in mainland China. Through our partner schools, students will be introduced to this study, and they will be asked to return the signed informed consents and leave their contact (e.g., email) in the reply slip to the research team if they are interested in taking part in the study. Furthermore, potential participants will be recruited through community referrals and advertising via social media and emails in Hong Kong and mainland China. Interested participants will be asked to complete the screening assessments, including Patient Health Questionnaire-9 (PHQ-9)⁵⁵ and Insomnia Severity Index (ISI)⁵⁶ via an online portal (Qualtrics). Participants who have an ISI score of no less than 15 and a PHQ-9 score between 4 and 20 will be further invited for diagnostic interview through telephone to screen for insomnia (International Statistical Classification of Diseases and Related Health Problems10th Revision Classification of Mental and Behavioral Disorders, ICD-10 Classification of Mental and Behavioral Disorders ⁵⁷), MDD and suicidality including ideation, plans and attempts (Mini International Neuropsychiatric Interview, MINI ⁵⁸). A potential participant who meets the inclusion criteria (see below) will be eligible to take part in the study.

Participants

Inclusion criteria and exclusion criteria for participants are as follows:

Inclusion criteria

- 1. Native Han youth in Hong Kong and mainland China, aged between15-25
- 2. A diagnosis of insomnia disorder measured by ICD-10 Classification of Mental and Behavioral Disorders
- 3. The presence of moderate or severe insomnia measured by a score of 15 or above on ISI
- 4. The presence of subclinical depression assessed by a score of more than 4 but less than 20 on PHQ-9
- 5. Access to smartphones

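### The mixed model for ISI, PHQ-9 and GAD-7 states no covariance across unevenly spaced visits; read plainly, its early standard errors are too large and its 12-month ones usually too small

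*Combined protocol and SAP*

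**What the plan says.** The Data Analysis section states: "The primary and secondary outcomes with continuous variables will be examined by using linear mixed-effects model (LMM) analysis". Changes and group differences are to be "tested by the MIXED module of Stata, with major measures at each time point nested within each participant". The effect estimate is the "Between-group difference in the estimated mean change from baseline to each time points from mixed models", with Cohen's d. Sex and insomnia severity are covariates. No random slope, residual covariance, visit-specific variance or robust standard error is mentioned, and the only sensitivity analyses concern missing data.

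Under Outcomes, two of the four primary outcomes are analysed this way ("change of insomnia symptoms measured by ISI" and "change of depressive symptoms measured by PHQ-9"), as is the secondary outcome GAD-7.

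The main visits are baseline, end of treatment, and 6 and 12 months. Under Assessments, all three scales are also collected "at post-session 2 and post-session 4". Modules unlock weekly (Intervention). The plan does not say whether the two in-treatment visits enter the model.

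The inclusion criteria restrict two of the scales at baseline: "The presence of moderate or severe insomnia measured by a score of 15 or above on ISI" and "a score of more than 4 but less than 20 on PHQ-9". GAD-7 has no entry limit.

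**The concern.** A random intercept with independent, equal-variance residuals gives every change-from-baseline contrast the same pooled error, apart from differences in numbers observed. That is right only if all visits share one variance and all pairs of visits share one correlation.

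Neither is likely here. Two measurements two weeks apart should agree more closely than two a year apart. Baseline ISI and PHQ-9 are cut by the entry rules while later scores are free. If correlation falls with time, a single pooled error is too large for the short-gap contrasts and tends to be too small for the longest.

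At stake are the p-values and intervals for two primary outcomes and one secondary outcome: lost power at post-treatment, and usually an optimistic test at 12 months, where durability is judged. With complete data the point estimates do not change; only their stated precision does.

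**Working it through.** **The plan's own figure.** The only sample-size figure concerns MDD. Freedman's log-rank formula (two-sided 5%, power 0.80, hazard ratio 0.5) needs (1.960 + 0.842)² × 9 = 70.6 events. Risks are 0.165 in controls and 1 − 0.835^0.5 = 0.0862 under treatment, mean 0.1256. So 70.6 / 0.1256 / 2 = 281.2, or 282 per arm, as stated. It uses no SD or correlation for ISI, PHQ-9 or GAD-7, so the present point does not touch it.

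**Formula.** With complete data and T visits with covariance Σ, the random-intercept model estimates one residual variance s² = trace(PΣ)/(T − 1), where P is the centring matrix. Then

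model SE / true SE at visit t = √[2s² / Var(Y_t − Y_0)],

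and a nominal 5% test rejects with probability 2Φ(−1.96 × ratio). A ratio above 1 means the standard error is too large.

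**Assumptions (none in the documents).** Visits at weeks 0, 2, 4, 6, 32 and 58, or the four main visits at 0, 6, 32 and 58. Correlation at a gap of g weeks = 0.8 × [0.3 + 0.7 exp(−g/26)]: 0.76 at 2 weeks, 0.69 at 6, 0.40 at 32 and 0.30 at 58.

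**Worked case, equal SDs, four visits.** The ratio reduces to √[(1 − mean correlation)/(1 − r_0t)]. The six pairwise correlations are 0.685, 0.404, 0.300, 0.446, 0.316 and 0.446, with mean 0.433.
- Post-treatment: √(0.567/0.315) = 1.34
- 6 months: √(0.567/0.596) = 0.98
- 12 months: √(0.567/0.700) = 0.90

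**All cases:**

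| Assumed SDs | Visits | Post-treatment | 6 months | 12 months | 12-month rejection |
|---|---|---|---|---|---|
| GAD-7-like: 4.5 throughout | six | 1.24 | 0.90 | 0.83 | 10.4% |
| | four | 1.34 | 0.98 | 0.90 | 7.8% |
| PHQ-9-like: 3.8, then 4.5 rising to 5 | six | 1.31 | 0.95 | 0.87 | 8.9% |
| | four | 1.45 | 1.03 | 0.92 | 7.1% |
| ISI-like: 3, then 5.5 | six | 1.28 | 1.03 | 0.97 | 5.9% |
| | four | 1.34 | 1.08 | 1.01 | 4.7% |

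With six visits the first in-treatment contrast has ratios of 1.39–1.55. If treatment takes the full 12-week access window, post-treatment ratios are 1.12–1.31 and 12-month ratios 0.85–1.02.

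**Power.** Take a contrast with 80% power under the correct standard error. At a ratio of 1.34 its power is Φ(2.80 − 1.96 × 1.34) = Φ(0.17), about 57%.

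**Entry cut-off alone.** SD 3 at baseline, 5.5 later, flat correlation 0.5: Var(Y_t − Y_0) = 9 + 30.25 − 16.5 = 22.75. With four visits s² = 13.25 and the ratio is √(26.5/22.75) = 1.08; with six, s² = 13.875 and it is √(27.75/22.75) = 1.10. Every standard error, including 12 months, is then too large.

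**Sensitivity.** Over 1,782 assumed SD and correlation sets, all with decay, and four timetables, the first post-baseline ratio was always above 1 (1.08–2.41). The 12-month standard error was more than 2% too small in 77–93% of sets and more than 2% too large in 1–8% (full range 0.75–1.11).

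**Simulation with dropout.** 354 per arm, six visits, 17–22% missing at 12 months, 500 runs per case. Random-intercept 12-month ratios were 0.78 (GAD-7-like), 0.82 (PHQ-9-like) and 0.92 (ISI-like), with rejection of 13.4%, 8.8% and 6.0%; the cut-off-only case gave 1.10. Unstructured covariance gave ratios of 0.95–1.07 at every visit and 12-month rejection of 4.0–5.6%. A separate simulation of 1,500 trials per scenario, with the severity covariate included and SDs growing over time, found the 12-month standard error 6–17% too small and 7–9% rejection; participant-clustered errors restored 4–6%.

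**The case against.** The strongest reply is that the plan never says random intercept only. Nesting in participant is also compatible with a by-visit residual covariance or robust errors, both available in Stata MIXED. That stands: the error is conditional on the plain reading. But if the structure is simply open, the model behind two primary outcomes can be settled after the data are seen, and the same sentence cures both problems.

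Four stronger readings are tempting, and the documents do not support them.
- A reader might infer that the entry cut-offs make the 12-month standard error too small. Alone they do the opposite (1.08–1.10). The shortfall comes from correlation decay and growing variance; the cut-off partly offsets it for ISI and PHQ-9.
- A reader might apply the cut-off argument to GAD-7. It has no entry limit, so only the visit-gap argument applies.
- A reader might extend the understatement to 6 months. The ratios there fall on both sides of 1 (0.90–1.08), so no such claim is made.
- A reader might treat the 12-month direction and size as fixed. No SDs or correlations are given, and the plan does not say whether the in-treatment visits are modelled. With four visits the ISI-like ratio is about 1.

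It is also fair that the early errors are conservative, and that the stated primary aim, MDD occurrence, is analysed by survival methods this does not touch.

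**Conclusion.** The point holds as a conditional one and merits a change to the plan. On the plain reading, and if correlation falls with time, standard errors for early contrasts are too large, by about 20–45% at post-treatment in most settings tried. The 12-month standard error is usually too small: about 5–17% with six visits, with a nominal 5% test rejecting about 6–10%, ISI at the low end and GAD-7 at the high end. With four visits the shortfall is about 8–10% for the PHQ-9-like and GAD-7-like cases and near nil for ISI. The early direction was consistent in every set with decay; the 12-month direction is likely, not certain. Insomnia remission (GEE), MDD occurrence and the sample size are unaffected.

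**What to change.** In the Data Analysis section:
1. State which visits enter the model for each scale, in particular whether the two in-treatment assessments do.
2. Fit visit as categorical with a group-by-visit interaction and the planned strata covariates.
3. Pre-specify an unstructured residual covariance by visit: in Stata mixed, residuals(unstructured, t(visit)) with the redundant random intercept suppressed, REML and small-sample degrees of freedom.
4. If that does not converge, use the random-intercept model with participant-clustered robust standard errors.

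The cost is SAP wording and one option in the code. Six visits need 6 × 7 / 2 = 21 covariance parameters, a light load for 708 participants. No data collection or sample size changes. The downside is wider 12-month intervals. In the dropout simulation the mean 12-month standard error rose from 0.410 to 0.446 (9%) for the ISI-like case, 0.359 to 0.430 (20%) for PHQ-9-like and 0.346 to 0.427 (23%) for GAD-7-like. Post-treatment intervals narrow in return (for example 0.392 to 0.313 for ISI-like).

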To address the limitations in the existing literature, we propose to conduct a RCT of targeted prevention intervention to validate the treatment effect of e-CBT-I on insomnia disorder and examine whether digitally delivered insomnia treatment can reduce the risk of depression in a high-risk group of youth population. To further explore the mechanisms underlying the association between insomnia treatment and depression, we will evaluate whether changes in candidate factors including insomnia symptoms, mood symptoms, sleep-related unhelpful thoughts and maladaptive behaviours, and circadian rhythm disruption will mediate the changes in depressive symptoms. On a conceptual level, the proposed interventional study will also allow us to further test the causal pathway between sleep disturbance and major depression, by intervening and treating insomnia as a preventive measure of depression. On a pragmatic level, digital approach to insomnia intervention for prevention of youth depression, if effective, may have important public health implications given its high accessibility to the young populations.

Methodology

Study Design

A randomized, assessor-blind, parallel group-controlled trial will be conducted in youth with insomnia and subclinical depression. All qualified participants will be randomly assigned via online system to receive e-CBT-I or health education (HE). Randomization will be stratified by sex and the severity of insomnia. Assessments will be carried out at baseline, post-treatment, 6-month follow-up and 12-month follow-up. Additional assessments will be given upon the completion of sessions 2 (post-session 2) and 4 (post-session 4) to evaluate sleep symptoms, mood symptoms, circadian rhythms and sleep parameters of participants. Saliva collection kit will be mailed to participants at baseline to collect their salivary cortisol and DNA, and at 12-month follow-up to collect their salivary DNA. Semi-structural individual interviews about user experience and satisfaction towards e-CBT-I intervention via phone calls will be given to part of the participants in e-CBT-I group after intervention.

Main hypothesis in the present study include:

1. Youth receiving e-CBT-I will have fewer onsets of depressive disorder and higher rates of remission in insomnia disorder at post-intervention, 6-month and 12-month compared

to those in control group.

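### The survival analysis names its event as current MDD, while the aim, the outcome and the censoring rule describe any MDD episode during follow-up

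*Combined protocol and SAP*

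**What the plan says.** The depression event is described in these places of the combined protocol and SAP.

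- Study Design, hypothesis 1: the intervention group will have "fewer onsets of depressive disorder and higher rates of remission in insomnia disorder at post-intervention, 6-month and 12-month compared" with control.
- Outcomes: one primary outcome is "occurrence of MDD conformed by MINI".
- Sample Size Estimation: the trial is sized on the occurrence of diagnosed depressive disorder, because "the primary aim of the current study was to prevent clinical depression". The planning rate of 16.5% is a cumulative one-year occurrence, built on the statement that "the incidence rate of depression is approximately 11% in the individuals with insomnia".
- Data Analysis, event: "Current MDD will be analyzed by the survival analysis and the Mentel-Cog log rank test".
- Data Analysis, censoring: the next sentence gives as an example a participant who "completed the trial without experiencing a depressive episode (12month follow-up after intervention".

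The Assessments section schedules diagnostic telephone interviews at post-treatment, 6 months and 12 months, "to examine whether they have current insomnia measured by ICD-10 Classification of Mental and Behavioral Disorders, MDD or suicidality measured by MINI". It gives no reference period for MDD and no rule for dating an episode. The only stated MDD look-back is in Exclusion criteria, item 5, at screening. That item lists current MDD and an earlier episode in the preceding two months as separate conditions.

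**The concern.** Onset, occurrence and having experienced an episode can all be one event: an MDD episode at some time after randomisation. Current MDD is a different quantity, namely being in an episode on the day of an interview. Someone who becomes depressed a month after the post-treatment call and has recovered before the next call has experienced an episode, so the censoring sentence does not treat that person as episode-free. Under the event sentence the same person has no event.

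This is the outcome on which the trial was sized and which carries the prevention aim. If the event is current status at three widely spaced calls, a long episode is more likely to be counted than a short one. A treatment that only shortened episodes would then lower the hazard ratio without changing the number of onsets. That would be a real benefit and not a false positive, but it is not the effect that hypothesis 1 states.

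**Working it through.** **1. The plan's own figure.** Inputs from Sample Size Estimation: control risk 0.165, hazard ratio 0.5, power 0.80, type I error 0.05 (sidedness is not stated; two-sided reproduces the figure), 1:1 allocation. Freedman's formula for the log-rank test:

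- Events: E = (1.96 + 0.8416)² × (1.5/0.5)² = 70.6
- Intervention risk: 1 − 0.835^0.5 = 0.0862
- N = 2 × 70.6 / (0.165 + 0.0862) = 562.4, that is 282 per arm
- Attrition: 282/0.6 = 470, as stated; 282/0.8 = 352.5, so 353 against the stated 354

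The arithmetic is correct. It takes 16.5% as cumulative occurrence and makes no explicit allowance for undetected episodes.

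**2. Gaps between interviews.** Six modules unlock weekly and access lasts 12 weeks (Intervention), so post-treatment falls about 1.5 to 3 months after baseline. The censoring rule counts the 12-month visit from the end of the intervention, and I take the 6-month visit to be counted the same way. The gaps are then 1.5, 6, 6 months (total 13.5) or 3, 6, 6 months (total 15).

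**3. Share of onsets not seen.** Assumptions outside the documents: onsets spread evenly, and a fixed episode length L. With look-back W at each interview, the missed share is Σ max(g − L − W, 0) / Σ g over the gaps g.

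| Episode length | No look-back (W = 0) | Two-month look-back (W = 2) |
|---|---|---|
| 3 months | (3+3)/13.5 = 44%; (3+3)/15 = 40% | (1+1)/13.5 = 15%; (1+1)/15 = 13% |
| 4 months | (2+2)/13.5 = 30%; (2+2)/15 = 27% | 0% |
| 6 months or more | 0% | 0% |

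The zeros depend on fixed lengths. With exponential lengths and λ = ln 2/median, the missed share is Σ[h − (1 − e^(−λh))/λ] / Σ g, where h = max(g − W, 0). For medians of 6 down to 2 months this gives 25-54% with no look-back and 11-27% with two months. Example (median 6, W = 0, gaps 1.5, 6, 6): (0.12 + 1.67 + 1.67)/13.5 = 26%.

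**4. Onset mixed with episode length.** Suppose onset is identical in both arms and treatment shortens episodes from 4 to 3 months, with no look-back. The ratio of detected events is (1 − 0.444)/(1 − 0.296) = 0.79, or (1 − 0.400)/(1 − 0.267) = 0.82. With a two-month look-back it is (1 − 0.148)/1 = 0.85, or (1 − 0.133)/1 = 0.87. Shortening from 12 to 8 months gives 1.00 in every case.

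**5. Power.** Follow-up runs beyond the one year behind the 16.5%. At a monthly control hazard of −ln(0.835)/12 and full detection, 282 per arm would give 79.0 events over 13.5 months or 87.0 over 15 months, against the 70.6 needed. Missed episodes pull the other way. The net result depends on episode length and on how the 11% was ascertained, and the documents give neither.

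**The case against.** The strongest reply is that one word is out of place and the rest of the plan is consistent. Onsets, occurrence and the censoring sentence all fit a first-episode outcome. So does the statement in Ethics & Other Considerations that participants diagnosed with MDD on assessment leave the study. In Assessments, the word current is clearly attached only to insomnia. The interviews may have asked about the whole interval, in which case the remedy is to replace two words.

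Most of this stands. A reader might infer that the plan has four competing event definitions. It does not: only current MDD departs from an otherwise consistent any-episode event. A reader might also infer that episodes were in fact missed, but the documents show a gap in the written definition and not what was asked on the calls. Nor does it follow that two analysts would necessarily count different events. That could happen only if past episodes were recorded; with current status alone they would count the same ones.

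The reply does not remove the point. The event sentence is the operative analysis rule, no passage supplies a look-back for MDD at follow-up, and the plan's own screening criterion separates current MDD from a recent past episode. It is therefore unsafe to read current as any episode since the last call.

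It is also fair that the losses shrink greatly with a modest look-back and vanish for long fixed-length episodes, so the no-look-back column is the literal worst case.

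**Conclusion.** The concern holds in a limited form. The event named in Data Analysis does not match the prevention aim, the primary outcome or the adjoining censoring rule. Followed literally, it omits episodes that begin and remit between interviews, and the resulting hazard ratio should not be reported as fewer onsets. This inconsistency needs no assumption.

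Its size does. Under even onsets and fixed lengths, the loss runs from 40-44% (3-month episodes, no look-back) to none (6 months or more, or 4 months or more with a two-month look-back).

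A reader might go further and infer that the trial is underpowered. The documents do not support that. The sample size reproduces, follow-up is longer than the one-year planning horizon, and if the 11% already reflects detection at study waves there is no loss at all. The change is worth making, with medium confidence, because actual conduct may have been wider than the wording.

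**What to change.** In Assessments and Data Analysis, state that each remaining follow-up MINI covers the whole period since the previous interview and records an approximate onset month. Define the event as the first MDD episode since randomisation, and use that definition in Study Design, Outcomes, Sample Size Estimation and Data Analysis. Keep current MDD at interview as a supportive outcome.

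Two situations change what is needed:

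- **Interval history is already collected.** Replace only the words current MDD in Data Analysis.
- **Some interviews recorded current status only.** This is possible, since version 5.0 is dated 08/12/2022. Do not combine the two kinds of data in one primary event. Analyse current MDD at scheduled interview for all participants, name it so, do not report it as onset or incidence, and state that the 16.5% planning rate assumes detection at those interviews.

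The cost is slightly longer calls that are already scheduled, plus one definition repeated across sections. The downside is some recall error for remitted episodes and their onset month, which is why current MDD is kept as supportive. No extra visits or participants are needed.
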